10.1 Response Criteria

Primary Outcome:

- 1) Improvement in cognitive function on the Digit Symbol Matching Test from pre-intervention to post-intervention.

Secondary Outcomes:

- 1) Improvement in daily function on the NeuroQOL Cognitive Function Scale from pre-intervention to post-intervention.
- 2) Improvement in cognitive function (improved accuracy and/or decreased response time) on Multiple Object Tracking, Digit Span Backwards, Simple RT, Choice RT, Letter/Number Switch, Gradual CPT from pre-intervention to post-intervention.
- 3) Improvement in daily function on the WHODAS 2.0 from pre-intervention to post-intervention.

Exploratory Outcomes:

- 1) Long-term improvement in cognition and daily function 4 weeks following completion of the intervention.
- 2) Improvement in cognitive function on the Visual Paired Associates Task.
- 3) Improvement in fatigue on the Modified Fatigue Impact Scale.
- 4) Improvement in mood symptoms on the PHQ-9 and GADS 7.

10.2 Duration of Response

Not applicable.

10.3 Progression-Free Survival

Not applicable.

10.4 Other Response Parameters

Not applicable.

11. Data Reporting / Regulatory Considerations

11.1 Data Collection

The data collection plan for this study is to utilize REDCap to capture all intervention, toxicity, efficacy, and adverse event data for all enrolled subjects. The REDCap database will be maintained by WCM and only members of the WCM research team will have access to the REDCap data.

Akili Interactive will have access to de-identified data related to gameplay during the video game intervention (metrics such as number of sessions played, time spent playing

the game, scores and performance, etc.). Gameplay data will be accessible via a dashboard linked to the iPad study devices; the device data will be connected to a unique ID number and will not be linked to participant PHI or identifiable information. Akili will not have access to participant medical records or identifiable information.

The computerized cognitive task battery is administered by a company called ManyBrains. They will have access to the scores collected during the cognitive tasks. Cognitive task data will be connected to a unique ID number and will not be linked to participant PHI or identifiable information. ManyBrains will not have access to participant medical records or identifiable information. They will store de-identified task scores in a research repository to be analyzed in aggregate form with other task scores to develop more optimized cognitive tasks in the future.

11.1.1 REDCap

REDCap (Research Electronic Data Capture) is a free data management software system that is fully supported by the Weill-Cornell Medical Center CTSC. It is a tool for the creation of customized, secure data management systems that include Web-based data-entry forms, reporting tools, and a full array of security features including user and group based privileges, authentication using institution LDAP system, with a full audit trail of data manipulation and export procedures. REDCap is maintained on CTSC-owned servers that are backed up nightly and support encrypted (SSL-based) connections. Nationally, the software is developed, enhanced and supported through a multi-institutional consortium led by the Vanderbilt University CTSA.

11.2 Regulatory Considerations

11.2.1 Institutional Review Board/Ethics Committee Approval

As required by local regulations, the Investigator will ensure all legal aspects are covered, and approval of the appropriate regulatory bodies obtained, before study initiation.

Before initiation of the study at each study center, the protocol, the ICF, other written material given to the patients, and any other relevant study documentation will be submitted to the appropriate Ethics Committee. Written approval of the study and all relevant study information must be obtained before the study center can be initiated or the IP is released to the Investigator. Any necessary extensions or renewals of IRB approval must be obtained for changes to the study, such as amendments to the protocol, the ICF, or other study documentation. The written approval of the IRB together with the approved ICF must be filed in the study files.

The Investigator will report promptly to the IRB any new information that may adversely affect the safety of the patients or the conduct of the study. The Investigator will submit written summaries of the study status to the IRB as required. On completion of the study, the IRB will be notified that the study has ended.

All agreed protocol amendments will be clearly recorded on a protocol amendment form and will be signed and dated by the original protocol approving signatories. All protocol

amendments will be submitted to the relevant institutional IRB for approval before implementation, as required by local regulations. The only exception will be when the amendment is necessary to eliminate an immediate hazard to the trial participants. In this case, the necessary action will be taken first, with the relevant protocol amendment following shortly thereafter.

Once protocol amendments or consent form modifications are implemented at the lead site, Weill Cornell Medicine, updated documents will be provided to participating sites, as applicable. Weill Cornell Medicine must approve all consent form changes prior to local IRB submission.

Relevant study documentation will be submitted to the regulatory authorities of the participating countries, according to local/national requirements, for review and approval before the beginning of the study. On completion of the study, the regulatory authorities will be notified that the study has ended.

11.2.2 Ethical Conduct of the Study

The Investigators and all parties involved should conduct this study in adherence to the ethical principles based on the Declaration of Helsinki, GCP, ICH guidelines and the applicable national and local laws and regulatory requirements.

This study will be conducted under a protocol reviewed and approved by the applicable ethics committees and investigations will be undertaken by scientifically and medically qualified persons, where the benefits of the study are in proportion to the risks.

11.2.3 Informed Consent

The investigator or qualified designee must obtain documented consent according to ICH-GCP and local regulations, as applicable, from each potential subject or each subject's legally authorized representative prior to participating in the research study. Subjects who agree to participate will sign the approved informed consent form and will be provided a copy of the signed document.

The initial ICF, any subsequent revised written ICF and any written information provided to the subject must be approved by IRB prior to use. The ICF will adhere to IRB requirements, applicable laws and regulations.

We will use verbal teach-back methods to verify comprehension of risks and benefits and capacity to consent to participation. For participants who screen as having moderate cognitive impairment (e.g., <2 SD below the normative mean on screening measures), we will use additional safeguards to verify comprehension of risks and benefits and study procedures, and to verify capacity to consent. The research staff member will conduct a formal interview (see attached questionnaire) to ensure that the participant comprehends study procedures, risks, and benefits. This questionnaire will ascertain whether the patient can communicate their choice; can attend to, understand, and recall the information discussed; and can weigh the risks and benefits to participating.

11.2.4 Compliance with Trial Registration and Results Posting Requirements

Under the terms of the Food and Drug Administration Modernization Act (FDAMA) and the Food and Drug Administration Amendments Act (FDAAA), the Sponsor-Investigator of the trial is solely responsible for determining whether the trial and its results are subject to the requirements for submission to <http://www.clinicaltrials.gov>. Information posted will allow subjects to identify potentially appropriate trials for their disease conditions and pursue participation by calling a central contact number for further information on appropriate trial locations and trial site contact information.

11.2.5 Record Retention

Essential documents are those documents that individually and collectively permit evaluation of the study and quality of the data produced. After completion of the study, all documents and data relating to the study will be kept in an orderly manner by the Investigator in a secure study file. Essential documents will be retained for 2 years after the final marketing approval in an ICH region or for at least 2 years since the discontinuation of clinical development of the IP. In addition, all subjects medical records and other source documentation will be kept for the maximum time permitted by the hospital, institution, or medical practice.

12. Statistical Considerations

12.1 Study Design/Endpoints

We will test the hypothesis that patients receiving the AKL-T01 intervention will have significantly enhanced improvement in cognition and daily functioning, relative to a waitlist control group.

- 1) Our primary cognitive measure will be change in performance on a Digit Symbol Matching Task from baseline (pre-intervention) to week 6 (post-intervention) in all participants randomized to the AKL-T01 intervention arm or the waitlist control arm.
- 2) Our primary daily functioning measure will be change in score on the NeuroQOL Cognitive Function scale from baseline (pre-intervention) to week 6 (post-intervention) in all participants randomized to the AKL-T01 intervention arm or the waitlist control arm.

We will use analysis of variance (ANOVA) to test for differences in 1) Digit Symbol Matching and 2) NeuroQOL change scores across the intervention and control arms.

A secondary outcome analyses will use ANOVA to test for group differences in change in performance on the remaining cognitive tasks (Multiple Object Tracking, Digit Span Backwards, Simple RT, Choice RT, Letter Number Switch) and group differences in the WHODAS 2.0, our secondary measure of daily functioning.

We will use the Holm-Bonferroni method to correct for multiple comparisons. An intent-to-treat approach will be used in for all of the analyses above, including outcomes in participants who did not complete the intervention.

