1.2.2 Secondary Objectives

1) Our main secondary objective is to investigate the efficacy of the AKL-T01 intervention relative to a waitlist control in improving functional outcomes. The main measure of daily functioning is the NeuroQOL Cognitive Function scale.

Additional Secondary Objectives:

2) A secondary objective of the study is to investigate the efficacy of the AKL-T01 intervention relative to a waitlist control in improving cognition across a range of domains, including sustained attention, cognitive control, working memory, and processing speed. We will assess these cognitive functions with a remotely-delivered task battery that, in addition to our primary Digit Symbol Matching Task, also includes the following tasks:

- Multiple Object Tracking
- Digit Span Backwards
- Simple Reaction Time
- Choice Reaction Time
- Letter-Number Switching
- Gradual Onset Continuous Performance Test

3) Another secondary objective of the study is to investigate the efficacy of the AKL-T01 intervention relative to a waitlist control in improving daily functioning and quality of life, as measured by the World Health Organization Disability Assessment Schedule (WHODAS). The WHODAS assesses the following domains of functioning that are relevant to our post-COVID sample:

- Cognition – understanding & communicating
- Mobility – moving & getting around
- Self-care – hygiene, dressing, eating & staying alone
- Getting along – interacting with other people
- Life activities – domestic responsibilities, leisure, work & school
- Participation – joining in community activities

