1.2.5 Secondary Endpoints

- 1) The main secondary endpoint for our measure of functional outcomes is mean change from pre-intervention (baseline) to post-intervention (week 6) on the NeuroQOL Cognitive Function Scale.

To assess efficacy of the intervention relative to the control, change scores from baseline to week 6 will be calculated separately and compared for the AKL-T01 intervention arm and the waitlist control for the NeuroQOL scale score.

Additional Secondary Endpoints:

- 2) Secondary endpoints for our measures of cognition is mean change in performance from pre-intervention (baseline) to post-intervention (week 6) on the following tasks: Multiple Object Tracking, Digit Span Backwards, Simple Reaction Time, Choice Reaction Time, Letter-Number Switching, and Gradual Onset Continuous Performance Test, and Visual Paired Associated Task.
- 3) The secondary endpoint for our measure of daily functioning is mean change in WHODAS 2.0 score from pre-intervention (baseline) to post-intervention (week 6).

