Participants will be aware of their assignment to study arm because it is not possible to blind them. The research team members conducting the study assessments will be blind to assignments. The care managers will not be blinded because it is not possible to blind them and it is necessary for them to know of a participant's assignment to assist in troubleshooting.

Our primary cognitive outcome will be measured by performance on a Digit Symbol Matching Task and our primary functional outcome will be measured by assessment score on the NeuroQOL scale. Additional cognitive tasks will be administered during the assessment visits to measure additional domains of cognition and daily functioning for our secondary and exploratory endpoint analyses. See Schedule of Assessments (Section 6.1) for list of assessments included in battery.

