12.2 Sample Size/Accrual Rate

Our target sample size will be 100 COVID-19 survivors. 50 participants will be randomized to the AKL-T01 intervention arm and 50 participants will be randomized to a waitlist control arm.

Our total enrollment to meet our target sample size of 100 participants will be 125. Based on previous research conducted at our institution, we anticipate ~20% of individuals will decide not to participate after meeting eligibility criteria.

As primary analysis will utilize linear mixed models (as implemented in lme4) to examine slope of symptom change, we utilized the simr package in R (4.0) to estimate power for the specified model assuming 50 participants per study arm in 100 simulated data sets. For standardized beta coefficient corresponding to Cohen's d of ~0.4, power exceeds 88% (95% confidence interval 80.0-93.6%) for the base case, and exceeds 80% under a range of conservative assumptions, with alpha=0.05 for the primary hypothesis test.

We expect enrollment to last approximately 12 months, yielding an accrual rate of ~10 participants per month.

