12.4 Analysis of Endpoints

12.4.1 Analysis of Primary Endpoints

Our primary cognitive measure will be change in performance on a Digit Symbol Matching Task from baseline (pre-intervention) to week 6 (post-intervention) in all participants randomized to the intervention or control arm. Our primary daily functioning measure will be change in score on the NeuroQOL Cognitive Function scale from baseline (pre-intervention) to week 6 (post-intervention) in all participants randomized to the intervention or control arm. We will use analysis of variance (ANOVA) to test for differences in Digit Symbol Matching and NeuroQOL change scores across the two arms.

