12.4.2 Analysis of Secondary Endpoints

Our secondary outcome analyses will use ANOVA to test for group differences in change in performance on the remaining cognitive tasks (Multiple Object Tracking, Digit Span Backwards, Simple RT, Choice RT, Letter Number Switch) and group differences in the WHODAS 2.0, our secondary measure of daily functioning.

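### NeuroQOL is tested as a primary endpoint in 12.4.1 but is secondary in the Protocol Summary, 1.2 and 10.1, and the Holm family in 12.1 is not named, so the Digit Symbol success threshold is not fixed

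*Combined protocol and SAP*

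**What the plan says.** **Digit Symbol as the only primary.** The Protocol Summary, 1.2.1 and 1.2.4 name Digit Symbol Matching, change from baseline to week 6, as the primary measure and name no other.

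**NeuroQOL as secondary.** Section 1.2.2 introduces it with "Our main secondary objective is to investigate the efficacy of the AKL-T01 intervention", and 1.2.5 with "The main secondary endpoint for our measure of functional outcomes is mean change". The Protocol Summary agrees with both. Section 10.1 puts "Improvement in daily function on the NeuroQOL Cognitive Function Scale from pre-intervention to post-intervention" first under its secondary outcomes.

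**NeuroQOL as primary.** Section 3.1 says "our primary functional outcome will be measured by assessment score on the NeuroQOL scale". Section 12.1 calls it the primary measure of daily functioning. Section 12.4.1, headed as the analysis of primary endpoints, uses ANOVA to "test for differences in Digit Symbol Matching and NeuroQOL change scores across the two arms". Section 12.4.2 lists the secondary tests as "Multiple Object Tracking, Digit Span Backwards, Simple RT, Choice RT, Letter Number Switch" plus WHODAS 2.0; NeuroQOL is not among them.

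**Multiplicity and power.** After listing all these tests, 12.1 says "We will use the Holm-Bonferroni method to correct for multiple comparisons". It does not say which tests are covered or whether one or both lead measures must succeed. Section 12.2 gives power "with alpha=0.05 for the primary hypothesis test", in the singular, and at no adjusted level.

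**The concern.** A Holm procedure is defined only once its members are listed, because the first-step threshold is the family-wise level divided by their number. Here the role of NeuroQOL and the extent of the family are both open, so the plan does not determine when the trial has succeeded on Digit Symbol.

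The ambiguity works in both directions. A Digit Symbol result can be a success under one section and a failure under another. Equally, Digit Symbol p=0.20 with NeuroQOL p=0.01 rejects one of two primary measures if 12.4.1 is read with Holm, but is a secondary finding after a failed primary under 1.2. The Group A and Group B labels in 7.11 would not stop a reading being settled after results are seen, because p-values are visible without unmasking the arms.

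The secondary list is unsettled too. Gradual CPT is secondary in 1.2.5 and 10.1 but is missing from the tests in 12.1 and 12.4.2. Visual Paired Associates is a secondary endpoint in the Protocol Summary and 1.2.5, but exploratory in 1.2.3, 1.2.6, 10.1 and the exploratory objectives of the Protocol Summary.

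**Working it through.** **Inputs from 12.2:** 50 per arm, d about 0.4, alpha 0.05, 100 simulated data sets, power 88% with interval 80.0-93.6%. **Assumptions:** two-sided tests (the documents do not state sidedness); test statistics correlated 0 to 0.5; the other endpoints' effects range from null to equal to that of Digit Symbol.

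**1. The plan's own figure.** The interval reproduces: the exact binomial 95% interval for 88 of 100 is 79.98% to 93.64%. It expresses simulation error only. The 88% cannot be reproduced, because the variance inputs of the mixed-model simulation are not given. For the ANOVA on change scores named in 12.1, with d=0.4 in change-score SD units, the noncentrality is 0.4 × √(50/2) = 2.0 on 98 degrees of freedom, and power is 50.8%. The results below are therefore shown for several base powers.

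**2. Thresholds.** Section 12.1 lists 2 lead measures + 5 tasks + WHODAS = 8 tests.
- Sole primary outside Holm: 0.05.
- Two primaries: 0.05/2 = 0.025.
- All eight tests: 0.05/8 = 0.00625. Adding Gradual CPT gives 0.05/9 = 0.0056, and adding Visual Paired Associates as well gives 0.05/10 = 0.005.

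**3. The same data under two readings.** Take Digit Symbol p=0.03 and NeuroQOL p=0.20. As sole primary, 0.03 ≤ 0.05: success. Under two-primary Holm the smallest p, 0.03, exceeds 0.025, so testing stops and neither is rejected. Had NeuroQOL been at or below 0.025, Digit Symbol would be tested at 0.05 in the second step and would pass. The readings therefore differ only when Digit Symbol lies between 0.025 and 0.05 and NeuroQOL is above 0.025.

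**4. How often, with two primaries and base 88%.** The noncentrality is 1.960 + 1.175 = 3.135, which gives power 81.4% at 0.025. With independent statistics:
- NeuroQOL null: (0.880 − 0.814) × 0.975 = 6.4% of trials change verdict; Holm power is 88.0 − 6.4 = 81.6%.
- NeuroQOL effect equal: (0.880 − 0.814) × (1 − 0.814) = 1.2%; Holm power is 86.8%.

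**5. Full Holm by simulation** (400,000 replicates, correlation 0 and 0.5, other effects null to equal):

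| Base power at 0.05 | Two primaries: power | Verdict changed | Eight tests: power | Verdict changed |
|---|---|---|---|---|
| 80% | 71-78% | 2-9% | 53-64% | 16-27% |
| 88% | 82-87% | 1-6% | 66-79% | 9-22% |
| 93.6% | 89-93% | 0.5-4% | 77-90% | 4-16% |

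**6. Error rate if Digit Symbol is tested at 0.05 and eight secondaries share a separate, ungated Holm family.** With independent statistics and no true effects, the chance of any false claim is 1 − 0.95² = 9.75%. At correlation 0.5 the simulation gives about 8.0%.

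**The case against.** The strongest defence is that "primary" in 3.1 and 12.1 means primary within its domain: 12.1 pairs a primary cognitive measure with a primary daily functioning measure, and calls WHODAS the secondary measure of daily functioning. That explains those two sections. It does not explain why 12.4.1 tests NeuroQOL under a heading for primary endpoints, or why 12.4.2 omits it.

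It is also fair to say that the readings are not equally supported. Sections 1.2.1 and 1.2.4 name one primary, 12.2 speaks of one primary test at 0.05, and 12.1 separates the secondary analyses from the two lead measures. A reader might infer from the position of the Holm sentence that Digit Symbol must clear 0.00625. No section says that primary and secondary tests share a family, so the documents do not support that as the intended rule; it is only not excluded.

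A reader might also infer that the two-primary loss is harmless because 82-87% lies inside 80.0-93.6%. That inference fails: the interval is Monte Carlo error at alpha 0.05, not a tolerance for a changed alpha.

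Finally, every power figure depends on an unverified base. That stands, and is why a range is shown.

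**Conclusion.** The contradiction is real and lies in the operative analysis text. The plan supports 0.05 best and 0.025 second as the first-step threshold for Digit Symbol, and does not decide between them. The power in 12.2 applies only to the first.

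At the stated 88%, reading 12.4.1 as two primaries costs about 1 to 6 percentage points of Digit Symbol power and changes the verdict in the same share of trials, a modest effect. The eight-test reading would change it in 9-22%, but has the least support. These figures assume two-sided tests and correlation 0 to 0.5, and move with the base as tabulated.

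A reader might go further and conclude that the trial is underpowered because of multiplicity. The documents do not support that: under their best-supported reading no adjustment applies to Digit Symbol. Whether 88% is itself sound is a separate question, since 12.1 names ANOVA and 12.2 a mixed model. The point should be corrected before analysis; it does not invalidate the design.

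**What to change.** In 3.1, 12.1 and 12.4.1, state that Digit Symbol Matching is the single primary endpoint, tested at 0.05 outside the Holm family, and state whether the test is one- or two-sided. Move NeuroQOL to 12.4.2 as the main secondary.

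Name the Holm family as eight secondary endpoints: NeuroQOL, the six tasks including Gradual CPT, and WHODAS 2.0. Specify one score per task, because 10.1 allows accuracy, response time or both. Test the family only if the primary succeeds; otherwise state that the chance of any false claim across primary and secondaries is about 8-10% when nothing works. List Visual Paired Associates as exploratory only.

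If two primaries are intended, say so in 1, 1.2 and 10.1, state whether one or both must succeed, and restate the 12.2 power at the resulting threshold.

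**Cost.** The recommended change is wording only, with no added patients or visits. NeuroQOL could no longer be claimed as a primary success. If its effect matched that of Digit Symbol at base 88%, its power would be about 66-79% in the ungated family, or 70-72% when gated with all effects equal, against 82-87% with two primaries. Two tests, NeuroQOL and Gradual CPT, join the six in 12.4.2. If those six would otherwise have formed their own family, the first-step threshold for the other secondaries falls from 0.05/6 = 0.0083 to 0.05/8 = 0.00625.
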